Primary objective: To investigate whether zoledronic acid (a widely used antiresorptive) reduces the risk of new clinical fractures, as compared with placebo, in older adults with a recent non-hip, non-vertebral fragility fracture.

Study design: 4-year, phase IV, multicenter, parallel-group, randomized, double-blind, placebo-controlled trial.

Study population: Adults aged 65 or older with a non-hip, non-vertebral fragility fracture in the past 2 years. Fragility fracture is defined as a fracture occurring after a fall from standing height or less.

Number of participants: 2900.

Investigational products: Two infusions of zoledronic acid (5 mg) or placebo, one at baseline and one at 24 months. Prior to infusion, participants will receive a loading dose of oral vitamin D (50,000 IU or 2.5 mg). Participants will also be prescribed monthly oral vitamin D (25,000 IU or 1.25 mg/month) for the duration of the trial.

Primary outcome: Time to first new clinical fracture.

Study period: Q1 2021 - Q1 2027.

Study Name: The Fragility Fracture Trial
Version No: 2
Date: 2020-10-04
EudraCT No: 2019-004766-17

2. Introduction

About 95,000 individuals suffered a major fracture in Sweden in 2017.^{1,2} In comparison, less than half that number, about 40,000, suffered a stroke or myocardial infarction.¹ The most serious type of fracture is the hip fracture, which is regarded as an end stage disease because 25% of hip fracture patients die within a year.^{3,4} Of surviving hip fracture patients, only a minority regain their pre-fracture level of physical functioning and quality of life.⁵ High mortality rates and reduced quality of life are also seen in patients with vertebral fractures.^{6,7} Thus, hip and vertebral fractures are serious threats to the health and independence of older people.

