7.1. Primary outcome

Due to the high clinical relevance of most fractures, the primary outcome will be time to first new clinical fracture (ICD-10-SE codes: S12-S52, S72, S82, M48.5, M49.5, M80.0A, M80.0J, and M80.0K). Clinical fracture will be defined as any fracture that comes to medical attention, excluding fractures of the facial bones, skull, hands, and feet (ICD-10-SE codes: S02, S62, and S92), which are not generally considered osteoporotic.¹⁰ For the same reason, pathological fractures (e.g., due to cancer or osteomyelitis) will be excluded. High-energy fractures will be included because these are also associated with low bone mineral density.^{11,43}

Participants will be asked about fractures at study contacts, which will take place every 6 months of follow-up (see Section 9). Participants will also have the possibility of reporting fractures to their study center between the scheduled contacts. Participants who withdraw will be asked if they wish to answer questions about incident fractures before they formally withdraw. The Swedish Fracture Register will also be used to trace fractures for patients who consent to registry follow-up.

Fractures identified through interview will be verified through review of medical records by the study site investigator, given that the participant consents to it. Due to limited resources, the sponsor/coordinating investigator will not adjudicate fractures or other outcomes. To reduce the amount of missing data in the 10-year post-study analysis, fractures will be traced centrally by the sponsor using the above-mentioned ICD-10-SE codes in the Swedish National Patient Register. This register records all diagnoses made in inpatient care in Sweden since 1987 and all outpatient secondary (i.e., non-primary) care since 2001.⁴⁴

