7.2. Secondary outcomes

The secondary outcomes are as follows:

1. Time to first non-vertebral fracture (ICD-10-SE: S22.2, S22.3, S22.4-S22.8, S32.1-S32.5, S42, S52, S72, S82)
2. Time to first new non-hip, non-vertebral fracture (ICD-10-SE: S22.2-S22.8, S32.1-S32.5, S42, S52, S72.3-S72.4, S82)
3. Time to first hip fracture (S72.0-S72.2)
4. Time to first new forearm fracture (S52)
5. Time to first clinical vertebral fracture (S12, S22.0, S22.1, S32.0, M48.5, M49.5, M80.0A, M80.0J, and M80.0K)
6. Time to death

Study Name: The Fragility Fracture Trial
Version No: 2
Date: 2020-10-04
EudraCT No: 2019-004766-17

7. Time to first new cardiovascular event (stroke or myocardial infarction) (ICD-10-SE: I21, I60-I64)
8. Time to first new cancer diagnosis (ICD-7-SE: 140-209)
9. Occurrence of fall from standing height or less (ICD-10-SE: W00, W01, W03, W04, W18) not resulting in fracture between baseline and 48 months

Hip fractures are included among non-vertebral fractures and forearm fractures are included among non-hip, non-vertebral fractures. However, hip fractures and forearm fractures will also be assessed separately because these are common and classic types of osteoporotic fractures. Fractures, myocardial infarction, stroke, and cancer events will be identified through self-report and verified by investigators through review of medical records. Participants will also have the possibility of reporting these outcomes to their study center between the scheduled study contacts. Participants who withdraw will be asked if they wish to answer questions about these outcomes before they formally withdraw.

In the 10-year follow-up, myocardial infarction and stroke will be traced using the above-mentioned ICD-10-SE codes in the National Patient Register, SWEDEHEART, and the Swedish Stroke Register. SWEDEHEART is a register that covers most patients in Sweden who are hospitalized for acute coronary syndrome, coronary interventions, or valvular interventions.⁴⁵ The Stroke Register is a register of Swedish stroke patients, although it does not have complete coverage of the population.⁴⁶ At the 10-year follow-up, cancer events will be identified through the Swedish Cancer Register, which records all new cases of cancer in Sweden since 1958.⁴⁷ Deaths will be identified through the Swedish Cause of Death Register and by reports from family members to study centers.⁴⁸

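### For the 4-year analysis of stroke or myocardial infarction and of cancer, the protocol gives no systematic register-based way to find events, so fatal events may be missed and censored

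*Protocol*

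**What the plan says.** Section 7.2 of the protocol sets out how the clinical events are found during the trial: "Fractures, myocardial infarction, stroke, and cancer events will be identified through self-report and verified by investigators through review of medical records". It adds a route between contacts: "Participants will also have the possibility of reporting these outcomes to their study center between the scheduled study contacts". Under section 9 the scheduled contacts are six months apart, up to month 48.

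The registers are placed in a later analysis. For the cardiovascular outcome: "In the 10-year follow-up, myocardial infarction and stroke will be traced using the above-mentioned ICD-10-SE codes in the National Patient Register". Two further sources, the Stroke Register and SWEDEHEART, are listed with it. For cancer: "At the 10-year follow-up, cancer events will be identified through the Swedish Cancer Register".

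Two other outcomes are treated differently. For death, no 10-year limit is attached: "Deaths will be identified through the Swedish Cause of Death Register and by reports from family members to study centers". For the primary outcome, section 7.1 gives a second source: "The Swedish Fracture Register will also be used to trace fractures for patients who consent to registry follow-up".

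Section 13.6 excludes from the efficacy analysis any event that neither registries nor medical records can verify. Registries therefore appear there as a means of confirming events, whereas section 7.2 names only medical records for that purpose.

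**The concern.** A participant who dies of a stroke or infarction between two contacts cannot report it. The same holds for a cancer diagnosed shortly before death. The death is counted under outcome 6. Unless someone else brings the event to the centre's notice, outcome 7 or 8 is recorded as not having occurred.

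Reduction of cancer, of cardiovascular disease and of death are secondary objectives 2, 3 and 4 in section 3.2. Whether a stroke, infarction or cancer is ascertained thus depends partly on survival, and survival is itself a hypothesised treatment effect. At stake are precision for two secondary outcomes and, if treatment acted differently on fatal and non-fatal events, the hazard ratio itself.

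**Working it through.** The protocol states no event rate, effect size or power for outcomes 7 and 8, so there is no figure of its own to reproduce. The main check is of the text.

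**1. What happens to an unreported fatal event.** Section 13 ends follow-up at death, withdrawal, loss to follow-up or last contact. Section 13.6 gives a participant without a recorded event that follow-up time. An unreported fatal stroke is therefore censored with no event.

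**2. Whether another route finds it.**
- *Proxy interview (sections 9 and 15.4).* A next of kin may answer if the participant cannot respond and has consented to this. No interview after a death is described.
- *Serious adverse events (sections 8.2 and 8.4).* Fatal, life-threatening, hospitalising or disabling events are reported once the investigator is aware of them. Nothing says that such a report is then counted as outcome 7 or 8.
- *Family reports and the Cause of Death Register (section 7.2).* These identify the death. Nothing says that the cause is searched for stroke, infarction or cancer.
- *Questions at withdrawal (section 7.2).* These help only if the participant withdraws formally and agrees to answer.

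Each route can recover events. None is a systematic search.

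**3. Whether a planned analysis would reveal the loss.** The informative-censoring sensitivity analysis in section 13.8 is confined to the primary outcome. The sensitivity analysis that adds unverified events concerns events already reported.

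**4. Illustrative size.** Let m be the fraction of events missed, equal in both arms (an assumption). The standard error of the log hazard ratio is proportional to 1/√(number of events), so its inflation is 1/√(1 − m) − 1:

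- m = 0.10: 1/√0.90 − 1 = 5.4%
- m = 0.20: 1/√0.80 − 1 = 11.8%
- m = 0.30: 1/√0.70 − 1 = 19.5%

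For power, use the protocol's 2900 participants, 5% dropout and two-sided 5% level. The placebo risk p and hazard ratio HR are assumed. The active-arm risk is 1 − (1 − p)^HR, as in Appendix 1. Then

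events = 2900 × 0.95 × (mean of the two risks) × (1 − m)

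power = Φ(√events × |ln HR| / 2 − 1.96)

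Example: p = 0.06 and HR = 0.75 give an active-arm risk of 0.0453, a mean of 0.0527 and 145 events with m = 0. Power is Φ(12.04 × 0.2877 / 2 − 1.96) = Φ(−0.23) = 41%.

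| Assumed 4-year placebo risk | Assumed HR | m = 0 | m = 0.10 | m = 0.20 | m = 0.30 |
|---|---|---|---|---|---|
| 6% | 0.75 | 41% | 38% | 34% | 31% |
| 10% | 0.75 | 61% | 57% | 52% | 47% |

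Across assumed risks of 4% to 10% and hazard ratios of 0.65 to 0.80, missing 20% of events costs about 3 to 10 percentage points of power. The same method applied to the protocol's fracture inputs returns its stated 227 events and its hip-fracture powers of 71% and 55%.

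**The case against.** The strongest reply is that several routes to these events exist. A fatal or hospitalised infarction or stroke is a serious adverse event, and section 12.2 has adverse events coded in ICD-10-SE. Families report deaths, and consented proxies can be interviewed. Section 13.6 contemplates registries in the efficacy analysis, and sections 9 and 12.2 have participants followed through registers from randomisation, with central collection by the sponsor. Ascertainment is the same in both arms and double-blind. All of this stands. It means that events may be missed, not that they will be, and that nobody can say how many.

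The reply does not remove the gap. Every route depends on someone bringing the event to the centre's notice, and no sentence makes a death or a lost contact trigger a search.

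A reader might infer more than the documents support:

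- *That self-report is the sole source.* The routes above contradict this.
- *That disabling events are lost.* A survivor can report at any later contact to month 48, or a consented proxy can. Only a participant who never responds again and has no proxy is lost this way.
- *That fractures are affected alike.* Section 2 says that "25% of hip fracture patients die within a year", which invites a count of hip fractures lost to early death. That figure describes hip-fracture patients generally, whose mean age the same section gives as 83. Trial participants must be ambulatory and community dwelling, with no previous hip fracture. The Swedish Fracture Register is a second source, and section 13.8 stresses the primary outcome for informative censoring. No minimum number of lost fractures follows.
- *That differing 4-year and 10-year counts are an error.* They would be two analyses with openly different sources.

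**Conclusion.** The concern holds in limited form. For outcomes 7 and 8 at 4 years, section 7.2 provides no systematic register-based ascertainment, and sections 7.2 and 13.6 differ on what registries are for. Fatal events, and events in participants who stop contact without a consented proxy, may be censored as non-events, and no planned sensitivity analysis would show it.

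The size cannot be derived from the documents. The 5% to 20% rise in standard error rests on an assumed 10% to 30% of events missed, equally in both arms. It is an illustration, not an estimate. Bias in the hazard ratio is possible if treatment affects fatal and non-fatal events differently, but neither its direction nor its size can be stated. The primary test is not in question. The change is still worth making because it concerns two secondary objectives and uses sources already planned.

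**What to change.** Reconcile sections 7.2 and 13.6 and state, before unblinding:

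- For participants who have not opted out of registry follow-up, the National Patient Register, SWEDEHEART, the Swedish Stroke Register, the Swedish Cancer Register and the cause of death in the Cause of Death Register are a second source for outcomes 7 and 8 through month 48.
- How the end of follow-up in section 13 is defined for these two outcomes when a participant has stopped contact but is still covered by the registers, so that events and time at risk come from the same period.
- The self-report-based result is kept as a sensitivity analysis.

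The registers are already named, and sections 12.1 and 12.2 already provide for sending identification lists to the sponsor and for central collection. The cost is waiting for register delivery before the main report and some extra record checks. Because the change bears on outcome ascertainment, it may also count as a substantial amendment needing approval under section 15.3. Some gap will remain: participants may opt out, and section 7.2 notes that the Stroke Register does not cover the whole population.

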7.3. Exploratory outcomes

Two exploratory outcomes will be assessed:

1. Change in body height (cm) from baseline to 24 months
2. Change in non-dominant hand grip strength (kg) from baseline to 24 months
3. Change in EQ-5D-5L summary score from baseline to 12, 24, 36 and 48 months
4. Change in EQ-5D-5L visual analogue scale from baseline to 12, 24, 36 and 48 months

Body height (without shoes) will be measured in centimeters using stadiometers at baseline and at 24 months. Hand-grip strength will be measured using dynamometers. Values will be rounded to one decimal place. These outcomes will not be assessed at 48 months because the last follow-up visit will be a telephone interview instead of a physical visit to save resources (see Section 9).

The EQ-5D scale will be used to assess health-related quality of life because it is short, generic (rather than disease-specific) and widely used. Two previous trials of zoledronic acid used the 3-level version the EQ-5D (i.e., the EQ-5D-3L),^{22,37} but the 5-level version (EQ-5D-

Study Name: The Fragility Fracture Trial
Version No: 2
Date: 2020-10-04
EudraCT No: 2019-004766-17

5L) will be used in the current trial so that smaller differences in patient-reported health status can be detected. The summary score will be derived from the Swedish Time Trade-off, experience-based value set.⁴⁹ The term “experience-based” refers to the instruction that respondents rate their current health state, rather than a hypothetical health state.⁴⁹ The EQ-5D-5L will be administered annually as a compromise between detail in results and time burden for participants. Both the summary score and the visual analogue scale will be rounded to 2 decimal places.

7.4. Safety outcomes

Based on previous trials of zoledronic acid and the Summary of Product Characteristics of Aclasta,^{17,19-21} the occurrence or worsening of the following pre-specified safety outcomes will be assessed:

1. Post-infusion symptoms
 - a. Influenza-like symptoms
 - b. Pyrexia
 - c. Myalgia
 - d. Headache
 - e. Arthralgia
2. Osteonecrosis of the jaw
3. Osteonecrosis (avascular necrosis) not of the jaw
4. Atypical femur fracture
5. Any atrial fibrillation
6. Serious atrial fibrillation
7. Re-operation of fracture
8. Delayed fracture healing
9. Renal failure
10. Hypocalcemia
11. Ocular event

In the 10-year follow-up, ICD-10-SE codes will be used to trace occurrences of atrial fibrillation (I48), renal failure (N17-N19), hypocalcemia (E835) femur shaft fractures (S722-S724), ocular events (H10-H22), osteonecrosis not of the jaw (M87), and inflammatory conditions of the jaw (K10.2) in Swedish National Patient Register.

8. Safety

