5.1. Inclusion criteria

To be included in the trial, patients must meet all of the following criteria:

1. Willing and able to provide written informed consent
2. Age ≥ 65 years
3. Ambulatory (i.e., able to walk without the assistance of another person; canes, walkers, and other assistive devices are permitted)

Study Name: The Fragility Fracture Trial
Version No: 2
Date: 2020-10-04
EudraCT No: 2019-004766-17

4. Community dwelling (i.e., living in own home or with friends or relatives)
5. Sustained a non-hip, non-vertebral fragility fracture in the past 2 years

Fragility fractures are defined as fractures occurring after a fall from standing height or less.¹⁰ In particular, these falls include the following International Classification of Diseases, 10th Revision, Swedish Version, (ICD-10-SE) codes:

- 1) Fall on same level involving ice and snow (W00)
- 2) Fall on same level from slipping, tripping and stumbling (W01)
- 3) Other fall on same level due to collision with, or pushing by, another person (W03)
- 4) Fall while being carried or supported by other persons (W04)
- 5) Other fall on same level (W18)

If the type of fall is unknown, it will be assumed *not* to have occurred after a fall from standing height or less.

Non-hip, non-vertebral fractures will include fractures of the clavicle, upper arm, forearm, ribs, pelvis, femur (excluding hip), or lower leg. Fractures of the face, skull, hands, and feet will be excluded, because these are not generally considered osteoporotic.¹⁰

The limit of no more than 2 years since fracture is based on two considerations. The first consideration is that the risk of sustaining a new fracture is highest soon after the initial fracture.^{38,39} For this reason, we expect zoledronic acid to have the greatest effect if it is administered as soon as possible. However, setting a short limit would reduce the number of potentially eligible participants, making the trial more difficult to carry out. Therefore, the time limit should not be set too short for pragmatic reasons.

A minimum duration between time of fracture and time of recruitment has not been set, because no delay in fracture healing was observed in a phase III trial of zoledronic acid in hip fracture patients.²⁰

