13.7. Safety analysis

All participants who receive at least one infusion will be included in a safety analysis. The occurrence of adverse events by the end of follow-up will be analyzed as the number of events and the number and percent of participants reporting at least one event. These data will

Study Name: The Fragility Fracture Trial
Version No: 2
Date: 2020-10-04
EudraCT No: 2019-004766-17

be presented by study group, seriousness, and causality (suspected/not suspected relation to study medication). The study groups will be compared using Fisher's exact test. For post-infusion symptoms occurring ≤ 3 days after infusion, data will be presented for both infusions in total and for events reported to have occurred ≤ 3 days after each infusion. In addition to specific adverse events, the composite safety outcomes of any adverse event, any serious adverse event, any serious adverse drug reaction, any unexpected adverse drug reaction, and any suspected unexpected serious adverse reaction will be reported. Laboratory values of serum calcium (low, <2.2 mmol/l; normal, 2.2-2.6; high, >2.6)⁶² will be analyzed in a shift table from before the first to before the second infusion. The number and percent with severe renal impairment (estimated glomerular filtration rate <35 ml/min/1.73m²) at Follow-Up Visit 1 will be presented. The mean and standard deviation change in estimated glomerular filtration rate from before the first to before the second infusion will be presented and compared between the groups using an independent-samples *t* test (Satterthwaite approximation of degrees of freedom).

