13.10. Sample size and power calculations

The trial will enroll 2900 patients, of whom 227 will need to sustain a clinical fracture during follow-up for the study to achieve 90% power to detect a 35% reduction in clinical fractures with the log-rank test (2-sided significance level of 5%). This calculation assumes a 4-year fracture risk of 10% in the placebo group and an overall dropout rate of 5% (due to withdrawal or loss to follow-up, i.e., deaths excluded). The details of the calculation can be found in Appendix 1. Appendix 2 provides a table of required sample sizes under varying assumptions. As shown, the required sample size is sensitive to changes in the assumed hazard ratio and the assumed fracture risk in the placebo group, but it is relatively insensitive to changes in the dropout rate.

To put the assumptions of the sample-size calculation in perspective, we note that 3 of 4 previous large trials of zoledronic acid had 90% power,^{19,20,22} whereas the fourth had 80% power.²¹ Incomplete follow-up (deaths excluded) was observed in 4% of women with osteopenia (6-year follow-up),²¹ 8% of men with osteoporosis (1-year follow-up),²² 13% of women with osteoporosis (3-year follow-up),¹⁹ and 17% of hip fracture patients (1.9-year

Study Name: The Fragility Fracture Trial
Version No: 2
Date: 2020-10-04
EudraCT No: 2019-004766-17

median follow-up).²⁰ Three of the trials that were powered to demonstrate effects on clinical fractures, and these showed effects of 27%,²¹ 33%,¹⁹ and 35%.²⁰

The assumed 4-year fracture risk of 10% was derived from data about the Swedish population that we have previously collected from the Swedish National Patient Register. We selected adults in Sweden who were aged 65 to 85 years and who suffered an initial fracture of the arm or lower leg in 2006 (ICD-10-SE codes: S42, S52, or S82). There were 10,361 such individuals who were not prescribed bone-protective treatment over the next 4 years. Their mean age was 74.9 years and 73% were women. Over the 4 years, 10.0% (n=1028) suffered a new fracture at a different skeletal site. We expect the restriction of the analysis to fractures of a different skeletal site to lead to an underestimation of the incidence of new fractures, but the restriction is necessary to avoid counting the same fracture twice. The distribution of fractures by skeletal site was as follows:

1. 457 fractures of the hip
2. 148 fractures of the upper arm
3. 125 fractures of the lower leg and foot joint

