- 72 International Conference on Harmonisation of Technical Requirements for Registration of Pharmaceuticals for Human Use. ICH harmonised tripartite guideline E3: structure and content of clinical study reports. 1995.
- 73 International Committee of Medical Journal Editors. Recommendations for the conduct, reporting, editing, and publication of scholarly work in medical journals. 2016.
- 74 Williamson S, Landeiro F, McConnell T et al. Costs of fragility hip fractures globally: a systematic review and meta-regression analysis. *Osteoporos Int* Osteoporosis

Study Name: The Fragility Fracture Trial
Version No: 2
Date: 2020-10-04
EudraCT No: 2019-004766-17

- International, 2017;28:2791–2800.
- 75 Schoenfeld D. Sample-size formula for the proportional-hazards regression model. *Biometrics* 1983;39:499–503.
- 76 Freedman LS. Tables of the number of patients required in clinical trials using the logrank test. *Stat Med* 1982;1:121–129.

Study Name: The Fragility Fracture Trial
Version No: 2
Date: 2020-10-04
EudraCT No: 2019-004766-17

19. Appendix 1: Sample Size Calculation

The first step in the sample size calculation is to calculate the number of fractures that need to be observed in the trial, because the log-rank test is powered by events rather than participants. According to Schoenfeld,⁷⁵ the necessary number of fractures (assuming 90% power, a 2-sided alpha of 5%, and a hazard ratio of 0.65) is

$$\frac{4(Z_{1-0.05/2} + Z_{0.90})^2}{\ln(0.65)^2} = 227.$$

Here, z_p is the p^{th} quantile of the standard normal distribution and $\ln(\cdot)$ is the natural logarithm.

The second step is to estimate the required number of participants, ignoring any early dropouts due to withdrawal. According to Schoenfeld,⁷⁵ a 10% fracture risk in the placebo group and a hazard ratio of 0.65 corresponds to an estimated risk of

$$1 - (1 - 0.10)^{0.65} = 0.06619$$

in the zoledronic acid group. With 227 fractures, the required number of participants becomes

$$\frac{227}{(0.10 + 0.06619)/2} = 2732.$$

The third step is to adjust the sample size of 2732 for dropouts. As suggested by Freedman,⁷⁶ this can be done simply by dividing the sample size by the proportion of non-dropouts:

$$\frac{2732}{1 - 0.05} = 2876.$$

For simplicity, we round this number up to 2900.

Study Name: The Fragility Fracture Trial
Version No: 2
Date: 2020-10-04
EudraCT No: 2019-004766-17

20. Appendix 2: Sample Sizes Under Varying Assumptions

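### Pooling healing events on index and new fractures over all infused participants attenuates any harm to healing, because the drug is expected to reduce new fractures

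*Protocol*

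**What the plan says.** Protocol Section 7.4 includes "7. Re-operation of fracture 8. Delayed fracture healing" in its list of pre-specified safety outcomes. It does not say which fracture is meant.

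Section 13.7 fixes the population, the measure and the test. On the population: "All participants who receive at least one infusion will be included in a safety analysis". Adverse events are "analyzed as the number of events and the number and percent of participants reporting at least one event". On the test: "The study groups will be compared using Fisher's exact test".

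Two other parts of the protocol bear on how the result would be read:

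- **New fractures are expected to differ by arm.** Appendix 1 states that "a 10% fracture risk in the placebo group and a hazard ratio of 0.65 corresponds to an estimated risk of" 0.06619 on zoledronic acid.
- **Every participant enters with a fracture.** Section 5.1 requires a non-hip, non-vertebral fragility fracture within the previous 2 years. It adds: "A minimum duration between time of fracture and time of recruitment has not been set, because no delay in fracture healing was observed" in an earlier trial of hip fracture patients.

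The subgroup presentations in Section 13.8 cover baseline characteristics and efficacy outcomes. No stated analysis separates healing events on the index fracture from those on a new fracture, or looks at healing by time since the index fracture.

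**The concern.** A healing complication can arise from two sources: the fracture that qualified the participant, or a fracture sustained during follow-up. Every participant in both arms has the first, so randomization balances it. The second is the primary outcome, which the drug is expected to reduce.

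For new fractures, the percentage of infused participants with an event is the risk of a new fracture multiplied by the risk of a healing complication given that fracture. The first factor favours zoledronic acid by design. A drug with no effect on healing would therefore tend to show fewer events, and a drug that impairs healing would show a smaller excess than its true per-fracture effect. The better the drug does on the primary outcome, the stronger this pull.

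At stake is the reading of two pre-specified safety outcomes in a population that may be infused soon after a fracture. A risk ratio near 1 could be taken as evidence that healing is unaffected when part of it reflects fracture prevention.

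**Working it through.** **Inputs from the protocol.** 2900 participants (Section 13.10) randomized 1:1 (Section 10), so 1450 per arm; 4-year placebo fracture risk 10%, hazard ratio 0.65, dropout 5% (Section 13.10 and Appendix 1).

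**Inputs not in the protocol, so assumed.** On placebo, q is the risk of a healing event per participant with a new fracture (5%, 10% or 20%), and i is the risk of a post-infusion healing event on the index fracture (0% to 5%). The true risk ratio RR is taken to be the same for index and new fractures, and all randomized participants are taken to be infused.

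**The plan's own figures reproduce.**

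- Events: 4(1.960 + 1.282)² / ln(0.65)² = 227.
- Zoledronic acid risk: 1 − 0.90^0.65 = 0.06619.
- Sample size: 227 / ((0.10 + 0.06619)/2) = 2732; 2732/0.95 = 2876, rounded up to 2900.

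**Expected participants with a new fracture.** 1450 × 0.10 = 145 on placebo and 1450 × 0.06619 = 96 on zoledronic acid, a ratio of 0.66. A 5% dropout in both arms lowers both counts and leaves the ratio unchanged.

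**Break-even harm.** The pooled risk is about i + 0.10q on placebo and RR(i + 0.06619q) on zoledronic acid. Setting them equal gives the per-fracture harm that would show as no difference:

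RR* = (i + 0.10q) / (i + 0.06619q)

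| q | i = 0% | i = 0.25% | i = 1% | i = 2% | i = 5% |
|---|---|---|---|---|---|
| 5% | 1.51 | 1.29 | 1.13 | 1.07 | 1.03 |
| 10% | 1.51 | 1.37 | 1.20 | 1.13 | 1.06 |
| 20% | 1.51 | 1.43 | 1.29 | 1.20 | 1.11 |

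Examples at q = 10%: for i = 0, 0.10/0.06619 = 1.51. For i = 1%, (0.01 + 0.01)/(0.01 + 0.006619) = 1.20. For i = 5%, (0.05 + 0.01)/(0.05 + 0.006619) = 1.06.

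**What the pooled table would show.** The apparent ratio is the true RR divided by RR*. At q = 10%:

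| True RR per fracture | i = 0% | i = 1% | i = 5% |
|---|---|---|---|
| 1.00 | 0.66 | 0.83 | 0.94 |
| 1.51 | 1.00 | 1.25 | 1.42 |
| 2.00 | 1.32 | 1.66 | 1.89 |

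In events with i = 0, a drug with no effect on healing gives 14.5 on placebo v 9.6 on zoledronic acid, and a true RR of 1.51 gives 14.5 v 14.5.

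**Power in the new-fractures-only case (i = 0, q = 10%), by simulation of the two-sided 5% Fisher test.** Over all infused participants, a true RR of 1.51 is declared significant about 3% of the time (about 1.5% in the direction of harm), and a true RR of 2.0 about 9%. With 145 v 96 participants with a new fracture as denominators, the figures are about 21% and 56%. The per-fracture comparison shows more, but it is not strong either.

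**The case against.** Comparing everyone infused, by assigned arm, is the usual safety analysis. It validly answers how many healing complications arise per treated participant, counting those avoided because a fracture was prevented. The obvious alternative, events per new fracture, conditions on something that happens after randomization. Fractures that occur despite the drug may differ from those on placebo, so that contrast could mislead in either direction. **This stands**, and it is why the pooled line should stay and the new-fracture line should be descriptive only.

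A reader might infer that the planned analysis would show no difference despite a 51% increase in harm. The documents do not support that as the expected result. It needs no events at all from index fractures, yet every participant has one and no minimum interval before infusion is set. With even modest index-fracture event rates the harm is diluted rather than cancelled.

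Two further inferences also go beyond the text. The protocol does not present these outcomes as its check on having no minimum interval; Section 7.4 attributes the list to earlier trials and the product information. Nor does it say that a participant whose index fracture has healed cannot have either event; re-operation in particular need not imply an unhealed fracture.

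Finally, event definitions and table splits may be set in a statistical analysis plan that is not shown, and Section 12.2 says that the eCRF did not yet exist, so a missing linking item is not itself a fault. Event dates (Section 8.1), fracture dates (Section 13.6) and time since index fracture (Section 13.2) might allow some linking later. **This stands in part.** Section 13.7 already fixes population, measure and test, and the lean toward apparent safety follows from those choices whenever new-fracture events are counted. Linking by date is less reliable than recording the fracture when the event is reported.

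**Conclusion.** The point holds as attenuation. Under Sections 7.4 and 13.7 as written, the comparison of the two healing outcomes is a valid net burden per treated participant, but as a measure of effect on healing it is pulled toward apparent safety. The direction follows from the protocol's own 10% v 6.6% new-fracture risks and holds whenever some events come from new fractures.

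The size rests on event rates that the protocol does not give and on a common risk ratio for index and new fractures. The fully hidden harm is a risk ratio of 1.51 at the extreme where every event is on a new fracture. With 10% of new fractures affected, it is about 1.20 at a 1% index-fracture event rate and about 1.06 at 5%. Over the whole assumed range with any index-fracture events, it lies between 1.03 and 1.43. If the sponsor means the index fracture only, the problem disappears, but the text does not say so.

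Efficacy conclusions are unaffected. This is a low-cost improvement to the safety analysis; it does not show that the planned comparison is invalid.

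**What to change.** 1. **Section 7.4:** state whether each of the two outcomes covers the index fracture, new fractures or both.
2. **eCRF (Sections 8.1 and 12.2):** add one item linking each such event to the index fracture or to a new one.
3. **Section 13.7:** keep the pooled all-infused comparison and add two lines.
   - Index-fracture events by arm over all infused participants. This is a randomized comparison that the number of new fractures does not affect. It can optionally be shown by time since index fracture, which Section 13.2 already collects.
   - New-fracture events by arm beside the number of new fractures, labelled descriptive.

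The cost is one data field and a few table rows, with no extra visits or participants. Each part will have fewer events than the pooled count, so estimates will be less precise, and the new-fracture line conditions on a post-randomization event and cannot be read as a randomized comparison.
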